1.3 Primary efficacy endpoint rationale

The primary objective of the study is to determine the efficiency of the therapy, in improving TBUT in eyes with DED due to MGD. This objective was chosen because a reduced TBUT is one of the most common signs of DED due to MGD. TBUT is considered abnormal when shorter than 10 seconds. The reason for choosing the margin of 1.5 second as a success criterion is following the recent IPL study performed by Lumenis and received an FDA approval. In the study the difference between the IPL arm and the control arm was 1.24 second. The IPL arm was 1.99 second in combination with MGX, and the sham +MGX was 0.75 meaning that the IPL alone was responsible to 1.24 second from baseline to 4 weeks follow-up (Effectiveness of Intense Pulsed Light for Improving Dry Eye Syndrome - Study Results - ClinicalTrials.gov).

Novoxel

Synopsis -Clinical Protocol Number: CLN 0798 Rev. 002

June 21, 2021

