4.2 Description of the Study

This study is a randomized, open-label, pilot clinical study comparing the Tixel device to an active control, which will be the LipiFlow System. The goal of this study is to compare between the Tixel device and the LipiFlow System and estimate the magnitude of the differences, if they exist, in terms of safety and effectiveness. A total of up to 30 patients (60 eyes) will be randomized for bilateral treatment and will be assigned in a 1:1 ratio into the Tixel treatment group or the control group at up to 2 study sites in Israel and/or Europe. The evaluator will be masked as to the randomization assignments. Both eyes will receive the same randomized assignment and both eyes of each patient will be evaluated at all time points. One eye will be selected as the designated "study eye" for statistical purposes: The study eye is the eye with the lower baseline TBUT. If both eyes have the same TBUT, the right eye will be the study eye. Outcome Measures

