7.4 Effectiveness Analyses

- Primary endpoint

The change from baseline at 4 weeks in TBUT in both study arms will be calculated along with 95% confidence interval. The Paired T-test or Signed rank test for two means (paired observations) (as is appropriate) will be applied for testing the statistical significance of the change within each study group.

Ho: $\mu h - \mu c < 1.5$

HA: $\mu h - \mu c \ge 1.5$

where μ 4w and μ base are the mean at 4 weeks and at baseline, respectively.

- Secondary effectiveness endpoints
- The change from baseline in the TBUT at 4 weeks will be analysed for non-inferiority with a margin of 1.5 using a one-sided two-sample t-test. The non-inferiority hypothesis set will be:

Ho: $\mu h - \mu c > 1.5$

HA: $\mu h - \mu c \leq 1.5$

where μ t and μ c are the mean changes from baseline for Tixel and control, respectively. Thus, the upper limit of the two one-sided 97.5% CI must be < 1.5 in order to demonstrate Tixel non-inferiority.

- The change from baseline at 12 weeks in TBUT will be calculated along with 95% confidence interval. The Paired T-test or Signed rank test for two means (paired observations) (as is appropriate) will be applied for testing the statistical significance of the changes within each study group.
- The change from baseline at 4 weeks and 12 weeks in the Ocular Surface Disease Index (OSDI) will be calculated along with 95% confidence interval. The Paired T-test or

Signed rank test for two means (paired observations) (as is appropriate) will be applied for testing the statistical significance of the changes within each study group.

• The change from baseline at 4 and 12 weeks in the MGS score will be calculated along with 95% confidence interval. The Paired T-test or Signed rank test for two means (paired observations) (as is appropriate) will be applied for testing the statistical significance of the change within each study group.

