7.7 Sample Size Justification

15 patients will be enrolled in each treatment group.

Sample size rationale:

The sample size calculation was based on an expected change from baseline at 4 weeks in TBUT score of 1.5 seconds with a standard deviation of 1.9 seconds within each study group.

Sample size justification:

A sample size of 15 will have 80% power to detect a difference in means of 1.5 assuming a standard deviation of differences of 1.9 (effect size of 0.78), using a paired t-test with a 0.05 two-sided significance level.

Reference:

7.8 **Poolability Analysis**

Patient demographic characteristics and background variables shall be summarized. To ensure poolability in case of more than one site, primary effectiveness will be analysed by site.

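### The 1.5 s non-inferiority margin has no LipiFlow basis and equals the whole change planned in each arm, so a pass would not show that Tixel keeps any of LipiFlow's effect

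*Combined protocol and SAP*

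**What the plan says.** Section 7.4 ranks the between-arm comparison as secondary. The 4-week TBUT change "will be analysed for non-inferiority with a margin of 1.5 using a one-sided two-sample t-test", and a confidence limit must fall below 1.5 "in order to demonstrate Tixel non-inferiority". The primary analysis in the same section is a separate test of change within each arm.

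The only reason given for 1.5 s is in section 1.3, which concerns the primary endpoint: "The reason for choosing the margin of 1.5 second as a success criterion" is a study of intense pulsed light (IPL). Of that study it says "In the study the difference between the IPL arm and the control arm was 1.24 second" and "The IPL arm was 1.99 second in combination with MGX, and the sham +MGX was 0.75". Section 7.4 reuses the number as a non-inferiority margin and gives no further reason.

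Section 7.7 sizes the trial on an "expected change from baseline at 4 weeks in TBUT score of 1.5 seconds" with an SD of 1.9 s in each group. It states 80% power for 15 patients per arm, "using a paired t-test with a 0.05 two-sided significance level".

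Section 4.2 describes a pilot with LipiFlow as the only control. Part of its goal is to "estimate the magnitude of the differences, if they exist, in terms of safety and effectiveness". Section 3 covers LipiFlow's indication, components and mechanism but reports no TBUT result for it.

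**The concern.** A non-inferiority margin is normally set smaller than the effect the control is known to have, so that a pass implies some of that effect is kept. Here the control's effect on TBUT is not documented, and the margin is as large as the entire change the plan expects from it. If LipiFlow gains the planned 1.5 s, the boundary of the null hypothesis is a Tixel gain of 0 s.

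The trial also cannot show whether LipiFlow itself worked, because there is no sham or untreated arm. The test sees only the difference between arms, so two devices that both do nothing look the same as two that both work.

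At stake is how a pass is reported. The word non-inferior, set beside a cleared device, invites the conclusion that Tixel is effective or shares LipiFlow's benefit. Nothing in section 7.4 limits it to the narrower statement that the test supports.

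**Working it through.** **Inputs.** Margin 1.5 s and a one-sided 97.5% limit (section 7.4). Planned change 1.5 s and SD 1.9 s in each group, 15 per arm (section 7.7). IPL study changes 1.99 s and 0.75 s (section 1.3).

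**The plan's own figure.** Paired t-test, n = 15, two-sided 0.05: non-centrality = (1.5/1.9) × √15 = 3.06 on 14 df. Power is 81.1%, or 80.2% at the printed effect size of 0.78. The stated 80% reproduces, so SD and n are being read as the sponsor meant them.

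**Margin against the available effects.**
- Margin / planned change per arm = 1.5/1.5 = 100%.
- Controlled IPL effect = 1.99 − 0.75 = 1.24 s; margin / effect = 1.5/1.24 = 121%.
- Margin / LipiFlow effect: cannot be computed, because the documents give no such effect.

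**Behaviour of the test in the intended direction** (lower limit of Tixel minus LipiFlow above −1.5 s).
- SE = 1.9 × √(2/15) = 0.694 s.
- t(0.975, 28 df) = 2.048; expected half-width = 2.048 × 0.694 = 1.42 s.
- P(pass) = P(T > 2.048), with T non-central t on 28 df and non-centrality (1.5 + true difference)/0.694.

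| True Tixel gain | True LipiFlow gain | Difference | P(pass) |
|---|---|---|---|
| any equal gain, including 0 s in both | same | 0 | 55.1% |
| 0.75 s | 1.5 s | −0.75 s | 18.0% |
| 0 s | 1.5 s | −1.5 s | 2.5% |

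At a true difference of 0, P(pass) is 75% if the SD is 1.5 s and 35% if it is 2.5 s. Both SDs are assumptions.

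The 0.75 s row is only an illustration. That value is the sham-plus-MGX change in the IPL study, and treating it as a no-effect gain here is an assumption.

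**Observed difference needed to pass.** If the observed pooled SD is exactly 1.9 s, Tixel may be at most 1.5 − 1.421 = 0.079 s below LipiFlow. With a true SD of 1.9 s, sampling variation in the SD moves this cutoff from about 0.40 s below LipiFlow to about 0.23 s above it (5th to 95th percentile).

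**The rule as printed.** Section 7.4 requires an upper limit below 1.5. If the difference is Tixel minus control, with longer TBUT better, that does not test for inferiority. At Tixel 0 s and LipiFlow 1.5 s the non-centrality is (1.5 + 1.5)/0.694 = 4.32, and the rule is met about 98.7% of the time. At 0.75 s against 1.5 s it is met about 88% of the time. Read as control minus Tixel, the printed rule is the intended one; the section does not settle which applies.

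**The case against.** The strongest reply is that the plan never says it will use this test to show that Tixel works. Evidence of change is left to the higher-ranked within-arm test. On the plan's inputs, a Tixel arm with zero gain passes at the nominal 2.5%. Passing at the same rate for any equal gain is a property of every two-arm non-inferiority test, whatever its margin.

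Much of this stands. Read beside a significant Tixel paired test against zero, the 55% with no change in either arm falls to about 2.5% (simulation). In the 0.75 s illustration, 18% falls to about 13%, or below 0.1% if the primary test is against the printed 1.5 s. That illustration is also weak: 0.75 s comes from another study and includes MGX, which section 6.5 does not list as a step in either arm. A reader might infer from it that an ineffective Tixel would often be declared non-inferior. The documents do not support that, because they give no no-effect TBUT gain for this trial.

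Two things do not fall away. The 2.5% holds only if LipiFlow truly gains at least 1.5 s, which no document supports and no arm can check. And the within-arm test has no untreated comparison, so it cannot separate a device effect from non-specific change. The general property of non-inferiority tests is the reason a margin needs a documented control effect, and this one has none.

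The absence of a power figure for the non-inferiority test is not in itself an error, since the trial was sized for another test.

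**Conclusion.** The point holds as a limit on interpretation. The margin is 100% of the change planned per arm and 121% of the controlled effect in the only study cited for 1.5 s. It rests on no LipiFlow TBUT effect in the documents. A pass, in the intended direction, excludes a Tixel deficit of 1.5 s or more and shows nothing about how much of LipiFlow's effect is kept. With 15 per arm and SD 1.9 s, it would occur about 55% of the time if neither device changed TBUT.

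The ratios come straight from the documents. The 55% assumes normal data, complete follow-up, the plan's SD and the intended direction.

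A reader might go further and infer that the trial is invalid or that the sponsor plans to claim benefit over sham. Neither follows: the test is secondary, the study is a pilot with an estimation goal, and section 7.4 makes no claim against sham. The wording should still be changed, because section 7.4 sets a formal pass rule without saying what a pass means.

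**What to change.** Replace the non-inferiority item in section 7.4, and carry the same text into the SAP that section 7.1 leaves open until database lock:

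> The between-arm result is the difference in mean 4-week TBUT change (Tixel minus LipiFlow) with its two-sided 95% CI. The comparison with the 1.5 s margin is exploratory and is met only if the lower limit of that CI is above −1.5 s. Meeting it means only that a deficit of 1.5 s or more is excluded. It will not be reported as evidence that Tixel is effective or preserves the LipiFlow effect.

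This replaces the printed upper-limit rule. The hypotheses above it, whose direction and symbols do not match their definitions, must be corrected in the same edit. The roughly 55% power at true equality may be noted in section 7.7 as context.

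The cost is wording only: no new patients, visits or analyses, since the margin comparison is read from the same interval. The sponsor gives up a formal secondary non-inferiority claim that had about 55% power at equality. The estimate remains imprecise, with an expected 95% CI half-width of about 1.4 s, but it serves the estimation goal in section 4.2 directly.

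### The TBUT non-inferiority rule points the wrong way: as written it passes a Tixel that is worse than LipiFlow and fails one that is better

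*Combined protocol and SAP*

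**What the plan says.** Section 7.4 lists this test first among the secondary effectiveness analyses: "The change from baseline in the TBUT at 4 weeks will be analysed for non-inferiority with a margin of 1.5 using a one-sided two-sample t-test". Its null hypothesis is a difference above 1.5 and its alternative a difference of 1.5 or less. The difference is printed as mu_h minus mu_c. The legend beneath it defines mu_t and mu_c, which "are the mean changes from baseline for Tixel and control, respectively". The decision rule follows: "Thus, the upper limit of the two one-sided 97.5% CI must be < 1.5 in order to demonstrate Tixel non-inferiority".

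Section 1.3 settles the direction of benefit: "TBUT is considered abnormal when shorter than 10 seconds", and "a reduced TBUT is one of the most common signs of DED due to MGD". The primary hypothesis in section 7.4 agrees. Its legend says that its means "are the mean at 4 weeks and at baseline, respectively", and it puts success at 1.5 or more, so improvement is a positive change.

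**The concern.** For an outcome where higher is better, non-inferiority means ruling out that the test device is worse than control by the margin or more. With the difference taken as test minus control, that is a statement about the lower confidence limit and the negative margin. The plan instead bounds the upper limit by the positive margin. Its null hypothesis contains the case where Tixel is better by more than 1.5 s, and its alternative contains every degree of Tixel inferiority, however large.

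All the other efficacy tests in section 7.4 are within-group, so this is the only one that compares the arms. Sections 1.2 and 4.2 make comparison with LipiFlow the purpose of the study. If the rule is applied as printed and the devices truly differ, it tends to reward the worse result and penalise the better one. Reversing it after the data have been seen would be a post hoc change to a prespecified success criterion.

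**Working it through.** **Inputs**

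- Margin: 1.5 s (section 7.4).
- Error rate: one-sided 0.025, from the 97.5% one-sided limit (section 7.4).
- Patients: 15 per arm (section 7.7), allocated 1:1 (section 4.2).
- SD of TBUT change: 1.9 s within each arm (section 7.7).
- Difference: D = mean change on Tixel minus mean change on control (legend in section 7.4). Positive D favours Tixel (section 1.3).

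**The plan's own figure.** Section 7.7 states 80% power for a paired t-test with n = 15, difference 1.5 s, SD 1.9 s and two-sided 0.05. The non-central t with 14 df and non-centrality (1.5/1.9) × √15 gives 81.1%; the printed effect size of 0.78 gives 80.2%. The figure reproduces, but it concerns the within-group test. No power is stated for the non-inferiority test.

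**Precision of the between-arm comparison**

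- SE = 1.9 × √(2/15) = 0.694 s.
- t(0.975, 28 df) = 2.048.
- Half-width = 2.048 × 0.694 = 1.42 s.

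With an observed SD of 1.9 s:

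- The printed rule passes when the observed difference + 1.42 < 1.5, that is, when it is below +0.08 s.
- The correct rule passes when the observed difference - 1.42 > -1.5, that is, when it is above -0.08 s.

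The two acceptance regions are mirror images.

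**Probability of declaring non-inferiority**, from the non-central t with 28 df:

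- Printed rule: P(T < -2.048) with non-centrality (D - 1.5)/0.694.
- Correct rule: P(T > 2.048) with non-centrality (D + 1.5)/0.694.

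For example, at D = -1.5 s the printed rule has non-centrality -3/0.694 = -4.32, which gives 98.7%. The correct rule has non-centrality 0, which gives 2.5%.

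| True D (Tixel - control) | Printed rule | Correct rule |
|---|---|---|
| -3 s | >99.9% | <0.1% |
| -1.5 s | 98.7% | 2.5% |
| -1.0 s | 93.5% | 10.3% |
| 0 | 55.1% | 55.1% |
| +1.0 s | 10.3% | 93.5% |
| +1.5 s | 2.5% | 98.7% |
| +3 s | <0.1% | >99.9% |

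Simulation with 200,000 trials at each of D = -3, -1.5, 0, +1.5 and +3 s agreed with these values to within 0.1 percentage point.

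**Sensitivity to the SD.** The values other than 1.9 s are assumptions. At a true D of -1.5 s the printed rule passes 99.96% of the time with SD 1.5, 88.7% with SD 2.5 and 75.3% with SD 3.0. The correct rule gives 2.5% in every case.

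**The case against.** The strongest defence is that the notation here is unreliable. The same expression, mu_h minus mu_c, is printed under the primary hypothesis, where the legend names different symbols, and mu_h is defined in neither place. It could be a copying slip or a fault in reading the equations from the PDF. If the intended difference were control minus Tixel, the hypotheses and the upper-limit rule would together form a valid non-inferiority test, so there may be a single swapped subtraction in an otherwise coherent rule. The decision sentence itself does not name the difference it bounds.

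That is a plausible account of how the error arose, but it does not rescue the text. The legend attached to this test defines mu_c as control, and control is the term subtracted. Replacing mu_h by mu_t leaves the rule reversed. Neither a control-minus-Tixel difference nor a lower limit of -1.5 appears anywhere in the documents. Whichever reading was meant, the wording has to change.

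Two limits on the impact do stand. First, the reversal needs a true difference between the devices: if they are equal, including equally ineffective, both rules pass 55.1% of the time. Second, this is a secondary analysis in an open-label pilot, and neither the within-group primary test nor the sample size based on it is affected. Section 7.1 defers further detail to a statistical analysis plan to be finalised before database lock. That offers an opportunity to correct the rule, but does not itself correct hypotheses already stated in the protocol.

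**Conclusion.** The rule is wrong as written and must be fixed. Read with its own legend and the stated direction of benefit, it tests whether Tixel fails to be better by 1.5 s, not whether Tixel is non-inferior. At the true non-inferiority boundary (Tixel 1.5 s worse), the chance of a false claim is 98.7% instead of the intended 2.5%; a Tixel truly 1.5 s better would pass only 2.5% of the time. These figures assume 15 evaluable patients per arm, normally distributed changes and a common SD of 1.9 s. The size varies with the SD; the reversal does not, because it follows from the sign alone.

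**What to change.** Restate the hypotheses in section 7.4, with mu_T and mu_C the mean 4-week changes in TBUT (follow-up minus baseline, in seconds) on Tixel and LipiFlow:

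- H0: mu_T - mu_C ≤ -1.5 s; HA: mu_T - mu_C > -1.5 s.
- Claim non-inferiority only if the lower one-sided 97.5% limit for mu_T - mu_C (the lower end of the two-sided 95% interval) is above -1.5 s.

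An equivalent and smaller edit is to define the difference explicitly as mu_C - mu_T and keep the upper limit below 1.5 s. Either version needs the symbols in the hypotheses to match the legend; the primary hypothesis needs the same tidying. Carry the corrected rule into the final statistical analysis plan, before any between-arm results are seen and before database lock.

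The cost is protocol and SAP wording, with no extra patients, visits or data. The correction restores the 2.5% error rate but does not add power: at a true difference of zero, 15 per arm gives 55.1%, and about 26 per arm would be needed for 80% by the normal approximation. That is a separate matter from the direction of the test.

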7.5 Handling of Missing data

Every effort will be made to complete follow-up for all patients and avoid missing data, in particular regarding the primary endpoint variable. However, in the event data is missing, multiple imputation will be used. Missing data in MGS score at 4 weeks will be imputed sequentially using multiple imputation (MI) technique. The imputation model will include age, gender and MGS score at earlier timepoints.

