4.2.1 Primary Effectiveness Endpoint

The primary effectiveness endpoint is the change from baseline to the 4-weeks follow up exam in Tear Break-Up Time (TBUT). TBUT must be assessed by a masked rater. The changes from baseline will be evaluated.

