4.2.2 Secondary Effectiveness Endpoints

- Change from baseline in patient symptoms using the Ocular Surface Disease Index (OSDI) at the 4-weeks and 12 weeks follow-up exam. OSDI is a scoring that evaluates patient symptoms based on a validated questionnaire [4].
- Changes from baseline to 4-weeks and the 12-weeks follow-up exam in Meibomian Gland Score (MGS). MGS must be assessed by a masked rater.

The MGS is determined for the lower eyelids using a device that applies a standardized pressure to an area including 5 glands (Meibomian Gland Evaluator, Johnson & Johnson Vision) while viewing the eyelid margin using a slit lamp microscope to determine the presence and quality of the gland secretions. A total of 15 glands in three lower eyelid zones (nasal, medial, temporal) will be evaluated. Each gland is graded from 0 to 3 (0 = no secretion, 1 = inspissated, 2 = cloudy, 3 = clear liquid). The maximum MGS score is 45 in each eye. The clinician performing the MGS must not be involved in the study procedure and must be blinded to which arm of the study the patient is randomized.

• Change from baseline to the 12-weeks follow-up exam in Tear Break Up Times (TBUT), as assessed by a masked rater.

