7.2 Analysis Populations

- Intent-to-Treat Population: The intent-to-treat (ITT) population includes all randomized patients. The primary and secondary efficacy analyses will be performed on the ITT population. Patients will be analysed as randomized.
- Per Protocol Population: The per protocol (PP) population includes all patients who have at least one follow-up visit, complete all the treatments as randomized, and have no major protocol deviations. Patients will be analysed as treated.

• Safety Population: The safety population will include all treated patients. The safety population will be analysed for all safety assessments. Patients will be analysed as treated. A summary table of number (%) of patients in each analysis population/set will be provided.

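### Section 7.5 gives an imputation model for 4-week MGS, a secondary endpoint, but none for the primary endpoint TBUT, and does not say how treatment arm is handled

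*Combined protocol and SAP*

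**What the plan says.** Section 7.5 asks for complete follow-up, "in particular regarding the primary endpoint variable", and then gives a general rule: "in the event data is missing, multiple imputation will be used". The only model it goes on to describe is for the Meibomian Gland Score: "Missing data in MGS score at 4 weeks will be imputed sequentially using multiple imputation (MI) technique". Its predictors follow: "The imputation model will include age, gender and MGS score at earlier timepoints".

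Section 4.2.1 makes the 4-week change in TBUT the primary effectiveness endpoint. Section 4.2.2 lists MGS among the secondary ones. On the analysis set, Section 7.2 says: "The primary and secondary efficacy analyses will be performed on the ITT population". That set is all randomized patients.

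In Section 7.4 the primary analysis is a paired t-test or signed rank test that "will be applied for testing the statistical significance of the change within each study group". The same kind of within-group test is planned for MGS, OSDI and 12-week TBUT. The one between-arm efficacy test is non-inferiority on 4-week TBUT.

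Section 7.1 leaves further detail to a statistical analysis plan to be finalised before database lock. No imputation model for TBUT appears anywhere in the text available for this review.

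**The concern.** There are two gaps.

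First, an ITT analysis of TBUT must do something about each patient without a 4-week value. The plan names the technique but not the model. Predictors, the role of baseline TBUT and the handling of arm are all open for the primary endpoint, yet are written down for a secondary one.

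Second, the model that is written omits treatment arm, although every efficacy test is either within an arm or between arms. A missing Tixel value would be drawn partly from LipiFlow patients, and the reverse. The arms are not alike at this visit. Under Section 6.4 the 4-week visit follows the last treatment, so Tixel patients have had three sessions and are about 8 weeks from Day 0, while LipiFlow patients have had one session and are 4 weeks from Day 0.

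Section 4.2 sets out to estimate the size of any difference between the devices. Pooled imputation shrinks that difference and pulls each within-arm change toward the other arm's.

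**Working it through.** **Inputs.** From Section 7.7: 15 patients per arm, expected gain 1.5 s, SD of change 1.9 s, paired t-test, two-sided 0.05, 80% power. The documents give no missing-data rate, no true arm difference and no MGS variability. The values used for missing rates and arm differences below are assumptions, shown as ranges.

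**The plan's own figure.** Exact paired-t power at n = 15 with difference 1.5 and SD 1.9 is 81.1% (80.2% at the stated effect size of 0.78). The 80% reproduces. With 14, 13 and 12 complete cases, power is 78.0%, 74.3% and 70.2%.

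**Available predictors.** Section 6.5 does not list MGS among the tests before Tixel treatments 2 and 3, so the only MGS before 4 weeks is probably the baseline value. The schedule in Appendix A is not in the available text, so this is not certain.

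**Size of the shift.** Let a fraction f be missing in each arm, completely at random, with true mean changes m1 and m2. A model without arm imputes on average (m1 + m2)/2. The completed mean of arm 1 is then

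(1 − f)·m1 + f·(m1 + m2)/2 = m1 − (f/2)·(m1 − m2).

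Arm 2 moves the same distance the other way, so the between-arm difference becomes (1 − f)·(m1 − m2).

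- MGS, the written model, assumed difference 5 points: 5 × (1/15)/2 = 0.17, 5 × (2/15)/2 = 0.33 and 5 × (3/15)/2 = 0.50 points per arm at 1, 2 and 3 of 15 missing. At 3 of 15, differences of 3 to 10 points give 0.3 to 1.0 points.
- TBUT, only if the same list is carried over, assumed difference 1.5 s: 0.05, 0.10 and 0.15 s per arm. The standard error is 1.9/√15 = 0.49 s, so these are about 0.1, 0.2 and 0.3 standard errors.

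**Simulation of the within-arm TBUT test.** 10,000 trials per setting; normal data, SD of change 1.9 s; assumed baseline/follow-up correlation 0.5 and missingness completely at random; 20 imputations by Bayesian linear regression on baseline, age and gender; Rubin's rules with small-sample degrees of freedom. The test is of zero change, as in the Section 7.7 power statement; the hypotheses printed in Section 7.4 use 1.5 instead.

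Bias without arm, gains 1.5 and 0 s: −0.048/+0.048 s at 1 missing per arm, −0.103/+0.096 s at 2, −0.150/+0.159 s at 3. With gains 1.5 and 0.75 s at 3 missing: −0.078/+0.075 s. With equal gains at 3 missing: −0.004/+0.004 s. With arm in the model, or separate models by arm, bias stays within 0.01 s.

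Power (%) in the arm gaining 1.5 s, as arm omitted / arm as covariate / separate model in each arm:

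| Other arm's gain | 1 of 15 missing | 2 of 15 | 3 of 15 |
|---|---|---|---|
| 0 s | 73.1 / 76.5 / 74.2 | 64.4 / 71.7 / 67.6 | 55.2 / 67.2 / 60.0 |
| 0.75 s | 76.4 / 77.0 / 75.1 | 70.6 / 72.7 / 68.4 | 63.7 / 66.7 / 59.9 |
| 1.5 s | 77.9 / 77.0 / 75.2 | 73.6 / 72.2 / 67.9 | 69.7 / 67.2 / 60.5 |

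Monte Carlo error is about 0.5 points for power and 0.005 s for bias.

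**Between-arm TBUT difference.** A separate run of 2,000 trials per setting with a true difference of 1.5 s gave 1.39, 1.32 and 1.21 s without arm at 1, 2 and 3 of 15 missing per arm. The formula gives 1.5 × (1 − f) = 1.40, 1.30 and 1.20 s. With arm the estimates were 1.50, 1.52 and 1.50 s.

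**The case against.** The strongest reply is that this is an incomplete specification in a 30-patient pilot, perhaps a slip with MGS written where TBUT was meant. TBUT is covered by the general sentence, and the later analysis plan can supply the model. The predictor list says what the model will include, not that nothing else enters, and since most tests are within group, imputing by group is a fair reading. Harm to TBUT needs several conditions together: the MGS list reused, arm left out, arms that truly differ, and values missing. Under Section 7.7's own assumption of 1.5 s in each group there is no bias, and the largest power loss needs an arm that gains nothing.

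Much of this stands as a limit on size. The deferral in Section 7.1 means the matter can still be settled, and the MGS shift cannot be called large or small because the documents give no MGS standard deviation. It does not remove the gap: the general sentence gives a technique without a model, and an analysis plan that expands Section 7.5 could inherit both faults.

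Two further points are fair. When data are missing completely at random, complete cases are also unbiased and have slightly more power (78%, 74%, 70%) than imputation with arm (about 77%, 72%, 67%), so these results are not an argument for imputation as such; the plan has already chosen it. The simulation also gave both arms the same SD and correlation, which favours one common model over separate ones.

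Nor is error inflation shown for non-inferiority. With Tixel truly worse by 1.5 s, a run of 4,000 trials per setting without arm gave false-positive rates of 2.6% to 3.2% against a nominal 2.5%. The problem shown is a distorted estimate and, when the arms differ, lost power in the better arm.

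**Conclusion.** The concern holds and should be fixed. That the primary endpoint has no imputation model, and that the one written model neither lists arm nor says it is fitted within arm, is plain from the text and depends on no assumption.

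The consequence is conditional. If the list is used as written, each arm's mean shifts by half the missing fraction times the true arm difference. It is nil when the arms respond alike and small when few values are missing. At the worst setting examined (3 of 15 missing per arm, the other arm gaining 0 s) it costs about 12 points of power (55.2% against 67.2%). The TBUT figures also require that the MGS predictor list be carried over, which Section 7.5 neither says nor rules out.

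**What to change.** Settle this in Section 7.5 or in the statistical analysis plan, before database lock:

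- Name the primary endpoint and its model, for example: *Missing TBUT at 4 weeks will be multiply imputed from a model with treatment arm, baseline TBUT, age and gender.*
- Add treatment arm to the MGS model.
- Write parallel models for OSDI and for the 12-week values.
- State how arm enters. With 15 patients per arm, one model with arm as a covariate is preferable to a separate model in each arm, which was also unbiased but had lower power (about 60% against 67% at 3 of 15 missing). This last choice is secondary; the essential step is that arm is accounted for.

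The cost is a few lines of text and code. If the arms respond alike, including arm loses about 1 to 3 points of power (77.9 − 77.0 = 0.9, 73.6 − 72.2 = 1.4 and 69.7 − 67.2 = 2.5). Visits, data collection and sample size do not change.
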